We propose imputation of post-failure BCVA by *last observation carried forward* (LOCF), followed by pooled regression (clustered robust standard errors on individual). We propose to do so only when BCVA is available at the time (study visit) at which treatment failure is declared. We will use all BCVA measurements until either treatment failure or completion of the trial and report the coefficient for randomization group, adjusting for baseline antimetabolite use and country.

We also propose to descriptively report mean, median BCVA (together with standard deviation and interquartile range) of patients at each visit. Actual BCVA will be reported in a descriptive analysis.

This collection of procedures serves as a template for all continuous outcomes for which we assess final values (below).

In Aim 3, these regression models will be examined on an intent to treat basis, so time/outcomes after treatment failure are included in the analyses.

The following regression analyses will be conducted following the templates above: statistical predictor will be randomization group, and we include fixed effects for baseline antimetabolite and country. A separate model will include country by treatment interaction. Treatment effects will be only reported by stratum when heterogeneity or interactions are found.

Final values of the following continuous outcome variables will be modeled following the template found above in this Planned Secondary Analyses with Alternative Outcomes section:

- **The CHAQ score**
 - For this quality-of-life measurement and the three specified immediately below, a separate analysis comparing the patient's baseline value with their value at the time of failure, 6 and 12 months will be considered.
- **The EQ-5D-Y score**
- **The CVFQ score**
- **The EYE-Q score**
- **The JADAS-10 and JADAS-27 scores**
- **Estimated ADA levels**

Final values of the following binary outcome variables will be modeled with log binomial regression following the similar template in the Planned Subsidiary Analyses of the Primary Model section:

- **The proportion of patients who exhibit one or more arthritis flares**
- **The proportion of patients who achieve an improvement in JADAS-10**
- **The proportion exhibiting macular edema**

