For continuous outcomes, plots of each measurement along with the outcome status will be prepared for each patient. Plots will include data for patients after any treatment failure, in a different color. We plan to separately examine patients using antimetabolites at baseline and those who were not. We will conduct linear mixed effects regression for these longitudinal outcomes, using time dependent covariates. The continuous variables of interest are:

- BCVA
- CHAQ score
- EYE-Q score
- JADAS-10 and JADAS-27 scores

Application of LASSO procedures to linear mixed models will be conducted with the R package `glmmlasso`.

Finally, a similar exploratory analysis will be used for the time to treatment failure (as defined earlier), again using LASSO regression with the same set of covariates. LASSO model selection will be implemented using the R package `coxnet`. We note that other model selection procedures (such as backwards stepwise regression) can be considered, provided uncorrected significance P-values are not reported after model selection.

3.1.3 Specific Aim 3

Primary analysis. The outcome variable is the proportion of people achieving corticosteroid-sparing controlled ocular inflammation at month 12 of the study. We propose log binomial regression, with randomization group as a covariate and fixed effects for baseline antimetabolite use and country. The analysis will follow the same template as in Specific Aim 1 for analysis of binary outcomes (including assessment of homogeneity by country). A linear binomial regression, with the identity link, will be used to calculate risk differences between groups. Significance will be assessed with a two-sided alpha of 0.05. The distinction between the analyses in Aims 1 and 3 are that in Aim 1, outcomes are reported at 6 and 12 months, censoring at treatment failure, while in Aim 3, outcomes are reported by intent-to-treat at 6 and 12 months, regardless of treatment changes in the event of treatment failure. We propose to use Firth bias correction in this log binomial regression, and additional information is provided below.

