3.2.2 Model validation and sensitivity

In all cases, standard statistical procedures will always be followed to ensure that no evidence indicates a violation of the assumptions underlying the statistical models used.

- We will assess the proportional hazards assumption for all Cox regressions using the methods given above (though we note that our primary hypothesis test is based on permutation).
- Also, we will examine Hosmer-Lemeshow goodness-of-fit tests for continuous predictors in binomial regressions. Linear models will always be assessed using residual plots (residuals vs. predicted values, and QQ plots), together with tests for normality (Anderson-Darling and Shapiro-Wilk procedures). Goodness of fit tests may be underpowered when they are needed the most (in small sample size studies). We do not propose formal thresholds for goodness-of-fit, but will add all such assessments to an analytic log, and make them available to the DSMC and statistical reviewers. Assessments of overdispersion will be conducted for count models.
- In the event of convergence difficulties in log binomial models we propose to use Poisson procedures with robust variance estimators. We propose to report the results of logistic regression in the event that all such procedures are unsuccessful. All such procedures will be reported.²²
- Jackknife influence estimates will be used in all analyses; single observations that could change the conclusions will always be reported; supplemental analyses dropping highly influential points will be reported at the discretion of the DSMC or statistical reviewers. We note that the presence of highly influential points does not invalidate the conclusions of a study, but such assessments contribute to the overall understanding of the trial. In our view, reporting the results of analyses dropping individual observations based on statistical outlier/influence tests *alone* is a dubious practice, in the absence of additional information about those outliers.
- Analyses in which our primary interest is in final outcomes (at either the 6 or 12 month timepoint for individuals who did not change treatment, or the time of failure for those who failed) will still be repeated using all available data (at all time points).

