- **The CVFQ score.** For sample size planning, we assume a T-test comparing change scores between the randomization groups. Assuming a standard deviation of 1.70 based on a validation study of the CVFQ,³² a total sample size of 118 and assumed 10% loss to follow-up by 12 months provides 80% power to detect a mean difference of 0.93 points.
- **The EYE-Q score.** For sample size planning, we assume a T-test comparing change scores between the randomization groups. Assuming a standard deviation of 0.75,⁸ the total sample size of 118 and assumed 10% loss to follow-up by 12 months provides approximately 80% power to detect a mean difference of 0.41 points.

- **The JADAS-10 score.** As before, we use a T-test comparing change scores between the two groups for sample size planning. Assuming a standard deviation of 8.23,¹⁰ the total sample size of 118 and assumed 10% loss to follow up by 12 months provides approximately 80% power to detect a mean difference of 4.5 points.
- **The JADAS-27 score.** Similarly, assuming a standard deviation of 8.16,¹⁰ the sample size of 118 and assumed 10% loss to follow-up by 12 months provides approximately 80% power to detect a mean difference of 4.5 points.
- **The ADA levels.** Assuming a standard deviation in ADA levels of 10,³³ the total sample size of 118 (and, the 10% assumed loss to follow-up by 12 months) suggest approximately 80% power to detect a difference of 5.5 in ADA serum levels in $\mu\text{g/mL}$.
- **The proportion of people with arthritis flares.** We assume (for sample size assessment) a test of proportions between the two randomization groups. Based on prior research, we expect 1% of those who continue adalimumab to have a flare by 6 months.²⁶ We anticipate 80% power to detect a difference of approximately 16% in the proportion of individuals experiencing arthritis flares among those who discontinue adalimumab (assuming a total sample size of 118 and 10% loss to follow-up by 12 months).
- **The proportion of patients who achieve an improvement in JADAS-10.** Assuming that 85% of those continuing on adalimumab will have an improvement in JADAS-10 score from baseline,³⁴ a total sample size of 118 (and 10% assumed loss to follow-up) provides approximately 80% power to detect a difference of at least 26% in the proportion of patients achieving an improvement between treatment groups.

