- **The proportion of people with macular edema.** We anticipate at most 1% of the individuals continuing treatment to develop macular edema, given its absence at baseline. We anticipate approximately 80% power to detect a difference of 15% (in absolute terms) in macular edema in the discontinuation arm (given 118 subjects).

The analyses for censoring at 6 months are similar to 12 months, with small decreases in detectable effect sizes due to assuming slightly shorter follow-up by month 12.

3.3.2.2 Specific Aim 2

Specific Aim 2 is exploratory, and is hypothesis generating. However, we present selected power analyses to illustrate the sufficiency of the sample size of the trial—fixed in Specific Aim 1—to inform regression models of the exploratory outcomes in Specific Aim 2.

For modeling the effect of the potentially predictive biomarker MRP8/14, we assume a

median split as a guide to power. Assuming approximately 50 uveitis flares among our patient population, we anticipate 80% power to detect a difference in MRP8/14 levels of 140 ng/ml (assuming a standard deviation of 250 ng/ml, based on previous studies).^{35,36}

For modeling the number of missed study treatment doses in the first 12 months, we anticipate over 80% power to detect a difference of 2.8 missed doses between the discontinuation and continuation groups (assuming 118 patients enrolled, and a standard deviation of 5).

For the time to failure outcome within 12 months, we anticipate 88% power to detect a hazard ratio of 2.0 between patients taking antimetabolites at baseline and those not using antimetabolites, assuming approximately equal numbers in each group (assuming 10% loss to follow-up).

3.3.2.3 Specific Aim 3

Primary Analysis

The proportion of people who achieved corticosteroid-sparing controlled ocular inflammation (Table 2) by month 6 of the study based on treatment intervention. For sample size planning, we assume a test of proportions between the two randomization groups. Based on prior research, we assume that 30% of those who discontinue adalimumab will have controlled ocular inflammation by month 6.²⁴ We anticipate over 80% power to detect a 29% difference between the two groups, based on 118 subjects.

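### SAP 3.1.1, 3.1.3 and 3.2.2 have no rule for an arm with zero events, so the planned relative risk and 95% CI for macular edema and 6-month arthritis flare are likelier than not to be unusable under the SAP's own 1% rates

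*SAP*

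**What the plan says.** **Expected rates.** SAP 3.3.2.1 expects very few events in the continue arm. For macular edema: "We anticipate at most 1% of the individuals continuing treatment to develop macular edema, given its absence at baseline". For arthritis flare: "we expect 1% of those who continue adalimumab to have a flare by 6 months".

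**Power.** For macular edema: "We anticipate approximately 80% power to detect a difference of 15% (in absolute terms) in macular edema in the discontinuation arm". For arthritis flare: "We anticipate 80% power to detect a difference of approximately 16% in the proportion of individuals experiencing arthritis flares". The arthritis line names its planning test: "We assume (for sample size assessment) a test of proportions between the two randomization groups". The macular edema line names none.

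**Analysis.** SAP 3.1.1 sends arthritis flare, JADAS-10 improvement and macular edema to one model: "Final values of the following binary outcome variables will be modeled with log binomial regression following the similar template". SAP 3.1.3 names log-binomial regression again for macular edema in Aim 3, and analyses arthritis flare there in the same way as in Aim 1.

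**Fallback.** SAP 3.2.2: "In the event of convergence difficulties in log binomial models we propose to use Poisson procedures with robust variance estimators". Logistic regression follows only if all of those procedures fail.

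**Related provisions.** SAP 3.1.3 says of the Aim 3 primary outcome: "We propose to use Firth bias correction in this log binomial regression, and additional information is provided below". SAP 3.2.2 prefers permutation-based tests where they can be used. SAP 3.5 makes everything after the primary analysis of each Aim descriptive, with 95% confidence intervals. No provision covers an arm with zero events.

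**The concern.** The model estimates a ratio of two risks. If one arm has no events, the maximum-likelihood relative risk is zero or infinite, and an interval built from the coefficient and its standard error means nothing. At the rates the SAP itself expects, this would be the usual situation for these two outcomes.

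The SAP then leaves the result to a software flag. On one branch the analyst reports an enormous ratio with an interval too wide to inform. On the other, the robust Poisson model reports an enormous ratio with a narrow interval, and a single event against none looks overwhelming. Because these outcomes are to be reported by estimate and interval, a wrong interval is a wrong result. The Firth correction, which would help, is assigned only to the Aim 3 primary outcome, where the SAP assumes control in 24 to 30% of the stopping arm and sparse events are not the difficulty.

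**Working it through.** **Inputs.** 118 patients, 59 per arm, 1:1 allocation, 10% loss (SAP 3.3.1), so 118 × 0.9 / 2 ≈ 53 per arm. Continue-arm rate 1%. Stopping-arm rate 1% + 15% = 16% (macular edema) or 1% + 16% = 17% (arthritis flare). Two-sided alpha 0.05.

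**1. The SAP's power figures.** Pooled test of proportions, with m the mean of the two rates:

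power = Φ{ [(p2 − p1)√n − 1.96√(2m(1−m))] / √(p1(1−p1) + p2(1−p2)) }

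Macular edema, n = 53: (0.15 × 7.280 − 1.96 × 0.3944) / 0.3799 = 0.840, giving 80%. The other cases, with exact Fisher power alongside:

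| Comparison | n per arm | Pooled z | Fisher |
|---|---|---|---|
| 1% vs 16% | 53 | 80% | 74% |
| 1% vs 16% | 59 | 84% | 81% |
| 1% vs 17% | 53 | 83% | 79% |
| 1% vs 17% | 59 | 87% | 85% |

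The stated figures are consistent with a test of proportions.

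**2. Chance of an empty continue arm.** P(0) = (1 − p)^n.

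| True rate | n = 59 | n = 53 |
|---|---|---|
| 0.5% | 0.744 | 0.767 |
| 1% | 0.553 | 0.587 |
| 2% (assumed) | 0.304 | 0.343 |

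For macular edema the SAP gives 1% as an upper limit, so 55 to 59% is a floor. For arthritis flare the 1% applies to 6 months only.

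**3. The log-binomial fit.** R's glm was run on 0/59 in the continue arm against 1, 2, 5 and 9 events out of 59. It reported convergence every time, with a log relative risk of about 18 and, for the fits whose standard errors were printed, values from about 2,200 to 4,700.

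**4. The robust Poisson fallback.** With x events in the non-empty arm, the sandwich variance of the log relative risk has two parts:
- non-empty arm: 1/x − 1/n;
- empty arm, fitted mean μ: nμ² / (nμ)² = 1/n, however small μ becomes.

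The sum is 1/x, so the robust standard error is 1/√x. The coefficient is simply where the iterations stop.

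| Table | Log RR | Robust SE | z | Fisher P |
|---|---|---|---|---|
| 0/59 vs 1/59 | 18.2 | 1.00 | 18 | 1.00 |
| 0/59 vs 2/59 | 17.9 | 0.71 | 25 | 0.50 |

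In the first row the reported 95% interval for the relative risk runs from about 1.2 × 10⁷ to 5.8 × 10⁸. A second program stopped at 20.4, giving z of about 21 for the same table. With two simulated covariates standing in for country and antimetabolite use, z was about 17, so adjustment does not cure it.

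**5. If the arms truly do not differ.** Exactly one arm is empty with probability 2q(1 − q), where q = P(0). At 1% per arm this is 2 × 0.553 × 0.447 = 0.494 (n = 59) or 2 × 0.587 × 0.413 = 0.485 (n = 53). If the fallback were used, its interval would exclude 1 in each of those trials.

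**The case against.** **The fallback may seldom be reached.** It starts only on convergence difficulties, and R's glm usually reports none here: 295 of 300 adjusted fits with an empty continue arm converged (covariate mix assumed). This stands. A reader might infer that the plan makes false significance the expected result; the documents do not support that. The 48 to 49% figure also needs equal true rates, which is not the SAP's planning assumption. But the other branch gives an unusable interval, so the gap remains either way.

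**Permutation tests and jackknife checks protect the reader.** In part. A permutation P-value for 0/59 against 1/59 is 1.00, and the jackknife reporting in SAP 3.2.2 would expose a result resting on one event, though not on two. Neither supplies an estimate or interval.

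**The likelihood still carries information.** True. A one-sided profile-likelihood limit exists: 0/59 against 9/59 gives a stop-to-continue relative risk of at least 4.3, and 0/59 against 1/59 at least 0.17, which is properly inconclusive. The SAP does not name this method, and R's default routine failed on these tables.

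**The power lines.** A reader might infer that true power is only 24 to 34%. That figure requires a Wald test and counts every empty-arm trial as a failure. The SAP names no Wald test for these outcomes. The likelihood-ratio test of the same model gives 91 to 95%, and Fisher's test 74 to 85%.

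**Discontinuation outcomes.** A reader might extend the point to discontinuation for safety or intolerance. SAP 3.1.3 names no model for these, and SAP 4.2 already compares discontinuation by Fisher's exact test.

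**Conclusion.** The concern holds for macular edema and for arthritis flare by 6 months. Under the SAP's own 1%, the continue arm is empty in about 55 to 59% of trials. The planned relative risk then has no finite estimate and no Wald 95% interval, and the stated fallback, if used, gives one that is falsely narrow. For macular edema the probability is higher if the true rate is below 1%. For arthritis flare at 12 months the SAP gives no rate; at an assumed 2% the probability is 30 to 34%, so the claim that an empty arm is likelier than not is not made there.

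These calculations use the planned arm sizes. Enrollment stopped early, and smaller arms would make an empty arm likelier at any given rate. Both outcomes are secondary and descriptive, and the primary result is unaffected. The stated power of about 80% is not shown to be wrong.

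**What to change.** In SAP 3.1.1, 3.1.3 and 3.2.2, add a rule for macular edema and arthritis flare when an arm has zero or very few events, with the threshold stated (for example, fewer than 5 events in either arm):

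1. Report the risk difference with a score (Miettinen-Nurminen) or exact 95% confidence interval, and a permutation or Fisher P-value.
2. If a relative risk is wanted, extend the Firth correction already named in 3.1.3 to these models, with profile-likelihood confidence intervals.
3. State that robust-variance Poisson regression is not used when an arm has zero events, whether or not the software flags a convergence problem.

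In 3.3.2.1, name the test behind the macular edema power figure; the figure itself can stay.

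The cost is SAP wording and a few lines of code, with no change for patients or procedures. The small downside is that the headline measure for these outcomes becomes a risk difference or a penalised relative risk. SAP version 5 already follows unmasking, so the revision history should date this change and say the same of it.

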3.4 Missing Data and loss to follow-up

Values of the primary study endpoint (time to treatment failure) can be analyzed when the individual is lost to follow-up, treating such individuals as having been censored after their last visit.

We will compare baseline characteristics of individuals lost to follow-up with those who continued in the trial, tabulating by age, sex, study site, and other covariates available at baseline. Significant predictors of loss to follow-up will be then included in models of the outcome variables and reported.

As suggested above, we will use a complete case analysis under the assumption of missingness completely at random for all secondary analyses. However, if values of covariates are missing for more than 15% of participants, then a sensitivity analysis will be conducted where missing covariates will be imputed using regression-based multiple imputation, using the `mice` package in R. Missing outcome data will be analyzed as last observation carried forward, and by sensitivity analysis in which we assess how extreme missing values would have to be in order to change the conclusions of the trial.

3.5 Multiple comparisons

No multiple comparison corrections will be made. All analyses following the primary analysis for each of the three Aims will be reported as descriptive and will be presented with 95% confidence intervals.

3.6 Interim Monitoring

The study will be monitored by a Data Safety Monitoring Committee (DSMC) appointed by the National Eye Institute. There will be in-person meetings in Year 01 and Year 05, and teleconference calls every 6 months in between, or as deemed necessary.

The DSMC will receive fully unmasked information at any time. Such reports will be prepared by the principal statistician following the instructions of the DSMC.

3.7 Stopping Guidance and Interim Analysis

Timing of the interim analysis. The Data and Safety Monitoring Committee will meet to review the interim efficacy data when 34 treatment failures have occurred. This represents approximately 40% of the anticipated 84 events expected in the trial based on the assumed median failure times used in the primary analysis sample size calculation (median 10 weeks in the stopping group, and 20 weeks in the adalimumab group). Timing the interim at 40% of events was chosen as a trade-off between having sufficient events to make interim efficacy, futility and safety analyses informative, and

timeliness with respect to the trial informing patient care in the event of stopping under one of the guidelines.

The DSMC will make one of the following recommendations:

- Continue the trial without modifications
- Continue the trial with study modifications
- Stop enrollment in the trial because of efficacy
- Stop enrollment in the trial because of futility
- Stop enrollment in the trial because of safety concerns

The DSMC will take into consideration (a) safety, (b) efficacy, (c) clinical importance, and (d) validity to make a final decision regarding stopping guidance implementation. If patient safety is not at risk, then consideration of secondary outcomes may outweigh the need for immediate reporting of the primary outcomes.

Efficacy. An unmasked interim analysis will be conducted when 34 treatment failures have occurred (the primary endpoint) to determine whether or not there is sufficient evidence to answer the primary aim and justify stopping additional enrollments.

We propose a group sequential boundary for judging the statistical significance of the primary outcome, allowing for the interim analysis. We propose a Kim-DeMets flexible alpha spending approach, implemented in the *gsDesign* package in R, with power function $\alpha^*(t^*)^\theta$, where $\theta = 1.75$ (θ chosen so that the two-sided *P*-value to stop the trial for efficacy is exactly 0.01 when 40% of events have occurred).³⁷ The detectable HR at the interim analysis is 2.4 at the original, 88% power. A nominal two-sided *P*-value of 0.044 at the final analysis will account for the proposed interim analysis under a group sequential design. The Appendix includes details of the parameters and output from R's *gsDesign* package.

Futility. Early discontinuation due to the unlikeliness of significant findings conditional on interim results may be considered, based on the original sample size considerations. For evaluating futility, we propose discontinuation for futility if the conditional power to detect a hazard ratio of 2.0 for placebo/adalimumab (the original design effect) is below 20% at the interim analysis.³⁸ Conditional power will be derived by simulation of the unobserved future patients according to the original alternative hypothesis. Our proposed futility guidance is one-sided, and is subordinate to efficacy analyses.

Harm. Stopping for harm will be done at the judgment of the DSMC. Harm will be assessed using adverse events, and especially serious adverse events. Ethical considerations require careful consideration and judgment by the DSMC.

All subjects who provide informed consent will be accounted for in this study. We will present the number lost to follow-up and the number of protocol deviations by arm.

If the proposed stopping criteria are met from an efficacy standpoint and there are no safety concerns, enrollment will stop and patients who have already enrolled will be followed through their final visits following the current study protocol. Should they experience a treatment failure, they will be unmasked per protocol and can continue to receive study-provided medication through Month 12. Their outcomes are valuable to overall results (primary and secondary analyses). The trial's main result provides information which informs decision-making regarding the risks of stopping adalimumab. Patients who are enrolled have already made the decision that they are comfortable being randomized to stopping therapy, so they are already past the point of making that decision. Even if unmasked and on placebo, it would not be expected that such a patient would resume therapy if they did not experience a recurrence of inflammation.

Unmasking active patients at such an interim point compromises patient and personnel efforts already initiated towards the trial, as well as their study data. Enrolled patients will remain in the study. Enrollment, however, shall stop in an effort to disseminate study results sooner so that patients considering discontinuation of adalimumab can make better informed decisions about future treatment. The DSMC may reconsider the decision regarding the protocol for patients who have not completed their follow-up if/when stopping guideline criteria are met.

For the Statistical Analysis Plan, adverse event reporting will be descriptive in nature. Serious adverse events (SAEs) are reported directly to the medical monitor within 24 hours of the time the study site learns of them, and the medical monitor will subsequently pass this information on to the DSMC Chair. The medical monitor will receive notification of the event, the timing of the event, a medical narrative from the study site, the site location, and the patient identification number. The statistician will report the study treatment assignment to the DSMC Chair if deemed necessary by the DSMC. If use of either intervention clearly results in an unacceptable increase in the risk of treatment failures, then the study will be stopped.

In the event of that the DSMC stops the trial early, for any reason, the final analysis will be conducted on the available data.

